If yes, please identify the activities and describe the plan to protect the privacy of participants. For example, a plan for protection of privacy might consist of conducting the assent process for an adolescent minor in a private setting, rather than in the presence of the minor's parent.

b) *Will the data collected in the course of the study be considered sensitive, e.g., include information about a mental health disorder, HIV status, or SS#?* Yes No

If yes, provide the rationale for why these data are needed:

If yes, could any of these data, if disclosed, damage financial standing, employability, insurability, or reputation?

Yes No

If yes, will a Certificate of Confidentiality be obtained? Yes No

Any person engaged in research collecting information about illegal conduct from human research subjects may apply for a Certificate of Confidentiality. NIH provides detailed instructions for investigators wishing to make an application at <http://grants.nih.gov/grants/policy/coc/index.htm>.

c) *Describe specific physical, administrative, and technical safeguards employed to secure data, e.g., limitation of access to data, use of locked file cabinets, protection of computer-based data systems. Data will be kept by one investigator ([name]) on a password-protected hard drive that only he has access to. No other investigators will have access to this data.*

d) *Will data that identify individual subjects be published or in any way be disclosed to third parties other than project personnel?*

Yes No

If yes, please explain here and incorporate the information in consent form:

28. Responsibility for costs of injury or illness related to research:

Will the sponsor or other funding agency be responsible for costs of injury or illness related to the research?

Yes No

If applicable, describe whether or not the sponsor will be responsible for investigational device removal if required:

If the sponsor or other funding agency will not be responsible for costs of injury or illness related to research, please complete:

a) *The reasons why the sponsor or funding agency is not accepting responsibility for research-related injury.*

All procedures for Secretin stimulation are standard of care

b) *Summary of risks as related to potential costs that could be incurred as a result of research-related injury or illness.*

The risk of using one dose of Secretin are extremely rare. Please see above.

c) *Describe reasons for requesting that DHMC or Dartmouth College provide coverage for research-related injury or illness, which is not standard policy.*

NA

29. Participant Remuneration:

Will participants be paid for their time, reimbursed for travel or meal expenses, or receive any sort of "gift" for participating in this study?

Yes No

If yes, please describe in detail:

Note: Participant remuneration is not considered a benefit of being in a research study. CPHS will consider the amount of payment in relation to the time needed and any inconvenience to participants. Payment, reimbursement, or gifts should not be in an amount that would be coercive to the participant population.

If study is to be done at the VA, specific questions need to be answered if a participant is being paid "in excess of reimbursement for travel." Please contact the CPHS office if you need more information.

30. Use of Drug or Biological Agent:

Respond to items below or check x No drug or biological agent involved.

List the drugs and biologic agents to be used in this study: Secretin (0.2 mcg/kg) in a single dose

Is each drug or biological agent approved by the FDA for the specific indication for which it is used in this study?

Drug or Biologic Agent: Secretin Yes **This drug is an FDA designated orphan drug "for use in conjunction with diagnostic procedures (excluding ERCP) for pancreatic disorders to increase pancreatic fluid secretions." In this study, secretin is being used under an IND granted to ChiRhoClin.**

Drug or Biologic Agent: _____ Yes No

If no, respond to a and b for each drug or biologic agent used for an unapproved indication:

a) *Briefly discuss the plan for the storage, dispensing, handling, and disposal of investigational and FDA-approved drugs, devices, and biologics. When these activities are being done by the investigator, include a description of the procedures for inventory control and documentation.*

DHMC Investigational Pharmacy is managing all study drugs.

Yes No

If No please describe management plan below.

b) Check and respond to one of the following statements for each drug or biologic agent:

If this study is being done under an Investigational New Drug (IND) application to the FDA please provide: IND # (Investigational New Drug): # 56821 and specify who holds the IND#: ChiRhoClin, Inc.

OR

If a drug or biologic agent or the combination of drugs or agents is not FDA approved for the indication for which it is used in this study, but an IND # has not been obtained, please **complete Attachment J**

31. Placebo vs. Standard Care:

Does any part of the study involve use of a placebo or procedures that are inconsistent with the standard of care at DHMC?

Yes No

If yes, respond to **Placebo: Attachment B**

32. Medical Device:

Respond to items below or check x No devices involved.

List the devices to be used in this study: NA

Is each device approved by the FDA for this indication?

Device: _____ Yes No

Device: _____ Yes No

If no or if FDA approval is pending, respond to a, b, and c for each device used for an unapproved indication.

a) Is the device provided free of charge by the sponsor? Yes No

b) Where are the devices used in the study stored? Who controls their use?

c) Respond to (1), (2), (3), or (4)

(1) If this study is being done under an Investigational Device Exemption (IDE) from the FDA please provide: IDE#: #__ or check here if the IDE is pending:

Also check the FDA Device HCFA Reimbursement Category:

A B2 B3

Please note: CPHS will not approve a study before an IDE # has been received.

OR

(2) If 510(k) notification for a device has been sent to FDA check here and either: provide a copy of the documentation verifying 510(k) clearance, or check here if 510(k) clearance is pending

OR

(3) If a device is exempt from IDE requirements, check here and provide a copy of a letter from the FDA or sponsor stating that the device is exempt from IDE requirements under 812.2(c).

OR

(4) If you are requesting a **nonsignificant risk** determination for a device from CPHS, please check here and complete **Attachment A**.

Please note: The CPHS may approve, disapprove, or require modifications in a protocol that has been approved or cleared by the FDA.

33. Conflict of Interest Review:

Dartmouth College, Dartmouth-Hitchcock Clinic, and Mary Hitchcock Memorial Hospital have adopted a policy on Conflict of Interest in Human Subject Research. Copies of the policy are available on the Dartmouth College, Office of Sponsored Projects web site at <http://www.dartmouth.edu/~osp/policies.html>.

Definitions:

“Conflict of interest” occurs when an independent observer may reasonably question whether an individual's professional actions or decisions are influenced by considerations of the individual's private interests, financial or otherwise.

Conflicting financial interests do not include:

- salary and benefits from Dartmouth College, Dartmouth-Hitchcock Clinic, and Mary Hitchcock Memorial Hospital;
- income from seminars, lectures, teaching engagements, or publishing sponsored by federal, state, or local entities, or from non-profit academic institutions, when the funds do not originate from corporate sources;
- income from service on advisory committees or review panels for governmental or nonprofit entities;
- investments in publicly-traded mutual funds;
- gifts and promotional items of nominal value; and
- meals and lodging for participation in professional meetings.

“Principal investigator or other key personnel” means the principal investigator and any other person, including students, who is responsible for the design, conduct, analysis, or reporting of research involving human subjects.

Instructions:

To assist institutional review of the proposed research for conflicts of interest, please respond to the question below.

With regard to this proposed research study, does the principal investigator or other key personnel, or any of their spouses, domestic partners, or dependent children, hold a financial interest that would

reasonably appear to affect or be affected by the proposed study, including but not limited to the following interests?

- a. *compensation for services (e.g., consulting fees or honoraria), or in-kind payments, other than from the researcher's primary employer, in the prior calendar year or projected over the next twelve months;*
- b. *royalty income or the right to receive future royalties under a patent license or copyright, when the proposed research is directly related to the licensed technology or work;*
- c. *equity interests (e.g., stocks, stock options or other ownership interests), including equity holdings where the value cannot readily be determined by reference to public prices;*
- d. *intellectual property rights (e.g., patents and copyrights), and royalties from such rights;*
- e. *gifts or funds available to the researcher from the sponsor of this study beyond the current project;*
- f. *funding expected to significantly exceed the projected costs of conducting this study; or*
- g. *another financial or private interest that may present a conflict of interest.*

*No: The Principal Investigator or other key personnel **do not** have any financial interests listed in a. -g. above.*

*x Yes: The Principal Investigator or other key personnel **do** have financial interests listed in items a. -g. above.*

Only if you have answered yes to the question above about study-specific financial interests for a member of the research team, please provide the following additional information.

Name of each individual with a listed financial interest: [name]

Each individual on the above list should complete a Conflict of Interest Disclosure Form for Human Subject Research. The disclosure should include only those financial interests that are specifically relevant to this research study.

The Conflict of Interest Disclosure Form for Human Subject Research is available on the CPHS website at the following url:

<http://www.dartmouth.edu/~cphs/tosubmit/forms/>

Please complete and sign the Conflict of Interest Disclosure Form for Human Subject Research form. In an envelope marked "Confidential", send the form to the Director of the Office of Sponsored Projects, using the following address:

CPHS/COI-HS, [name].

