Funding Source (Sponsor): ChiRhoClin, Inc, and ChiRhoClin Research Institute. This is an investigator-initiated project. ChiRhoClin, Inc. will supply the drug, Secretin. [name] will also receive a small grant from the ChiRhoClin Research Institute to support the research coordinator's salary.

1. Abstract.

Provide an abstract of the proposed research in language that can be understood by a non-scientist. The abstract should summarize the objectives of this project and the procedures to be used, with an emphasis on what will happen to the subjects. (Maximum 250 words)

Pancreatic ~~anastomotic~~-leaks complicate pancreatic resection in approximately 20% of cases. The pancreatic anastomosis or repair has been referred to as the Achilles heel of pancreatic surgery. Unfortunately, despite recognition of this problem and multiple operative techniques proposed to prevent this complication, leaks continue to represent a major cause of morbidity for patients undergoing pancreatic surgery. Treatment of leaks often requires nutritional support with total parenteral nutrition to diminish the leak in addition to invasive interventions to contain the leak with drains, stents or in severe cases, reoperation. Experiential data suggest that intra-operative infusions of secretin, a naturally occurring hormone that stimulates bicarbonate release from the pancreas, following resection but just prior to abdomen closure, may identify a leak if present. If secretin can demonstrate evidence of leaking intra-operatively, the pancreatic duct leak may be able to be fixed prior to abdominal closure. We aim to determine if giving an intra-operative infusion of secretin will allow for identification and treatment of leaks after pancreatic reconstruction and prior to abdominal closure, leading to a reduction in the rate of pancreatic ~~anastomotic~~-leaks requiring intervention. We will perform a double-blind, randomized pilot study of 176 patients undergoing pancreatic resection (pancreaticoduodenectomy and distal pancreatectomy) at Dartmouth-Hitchcock Medical Center. 88 of those patients will receive an intraoperative secretin infusion prior to abdominal closure and 88 will receive a saline placebo. Our primary outcome of interest will be the rate of pancreas duct leaks in each group as measured by the amount of amylase present in the surgical drains on or after post operative day (POD)# 3 following surgery.

2. Objectives & Hypotheses:

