C) This would be a randomized, double-blind, placebo controlled trial. 1/2 of the patients would receive intra-operative secretin, the other half would receive saline placebo. Both the surgeon and patient would be blinded to the randomization assignment. The advantage of giving secretin would be that it may allow for the identification of a leak intra-operatively and subsequently allow for repair if the leak was identified prior to abdominal wall closure. While the safety profile of the drug is excellent, receiving the medication could theoretically cause an increased intraductal pressure which may cause a leak when one was not already present.

D) Human subjects are needed to evaluate intra-operative, intravenous secretin in patients undergoing pancreatic duct resection.

4. Design, procedures, materials and methods:

Use a level of detail similar to what would be used when submitting an article for publication in a peer reviewed journal. Explain the study procedures, data collection, and analysis process. Please define terms and explain concepts which might be confusing to reviewers who are not expert in the area of the study. If a formal protocol for the study exists, page references to the protocol are acceptable.

This study design is a prospective, double-blind, randomized-controlled trial. We will enroll patients in our institution undergoing pancreatic resection to receive either 1) one dose weight-based Secretin to be given once the closure of the pancreatic resection margin is complete 2) saline placebo.

Consent and basic demographics will be garnered by the physician in an office visit once the surgery has been scheduled and consent for the surgery is being obtained. The consent will be validated by the treating surgeon in the pre-procedure area on the day of the surgery.

The patient will undergo the scheduled surgery. Once the pancreatic anastomosis has been deemed acceptable by the attending physician, but prior to abdominal closure, the patient will be randomized to receive either Secretin (0.2 mcg/kg) or saline placebo. The attending surgeon will be blinded to this assignment.

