10 minutes after receiving the Secretin or placebo, the attending surgeon will examine the anastomosis or repaired cut edge of the pancreas to determine if leakage of pancreatic fluid is noted, leak location(s), type (side branch/main duct), color of the fluid and whether any further intervention was performed in an effort to close the leak. Specifics of operative intervention will be documented. The patient will then undergo standard surgical closure of the abdomen.

As is standard of care at DHMC, surgical drains will be placed adjacent to the anastomosis and drain amylase output will be checked on POD #1 through POD#5. Pancreatic leak is defined according to the International Study Group of Pancreatic Fistula (ISGPF) definition as a clinically relevant postoperative pancreatic fistula is now redefined as a drain output of any measurable volume of fluid with an amylase level >3 times the upper limit of institutional normal serum amylase activity, associated with a clinically relevant development/condition related directly to the postoperative pancreatic fistula. Randomization assignments will be revealed once the patient has been discharged from the hospital following their initial surgical intervention. A follow-up visit with the patient two weeks following discharge, will evaluate for any evidence of ongoing pancreatic duct leak.

The patient will also be followed for thirty (30) days after secretin/placebo administration by the research team to assess for a pancreatic leak and sequelae of a leak, - intra abdominal deep soft tissue infection, surgical site infection, hemorrhage, IR (interventional radiology) drain placement, or reoperation. This will be accomplished by telephone and/or by chart review Patients discharge date will be followed for the study. If no secretin/placebo is administered, the patient will not be followed on the study.

If any of the above are noted during the 30 days following secretin/placebo administration the following will be used to assess causality:

Causality

The following 4-point scale will be used for rating the causal relationship of the AE to the investigational product:

Unrelated: Clearly and incontrovertibly due to extraneous causes, and does not meet criteria listed under unlikely, possible, or probable.

- Unlikely:** Does not follow a reasonable temporal sequence from administration. May have been produced by the patient's clinical state or by environmental factors or other therapies administered.

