- Possible:** Follows as reasonable temporal sequence from administration. May have been produced by the patient's clinical state or by environmental factors or other therapies administered.
- Probable:** Clear-cut temporal association with improvement or cessation of test drug or reduction in dose. Reappears upon re-challenge. Follows a known pattern or response to test drug.

The primary outcome of interest will be the presence of pancreatic leaks based on the amount of drain amylase on or after POD#3. Secondary outcomes will include: 1) technical interventions intraoperatively directed to leak closure or manipulation of the anastomosis following Secretin or placebo stimulation 2) length of stay as a surrogate to complication severity after pancreatic surgery.

Patient demographics, risk factors, operative technique, randomization assignment and outcome data will be recorded on standard case report forms – **See Case Report Forms in Appendix**. Data will be stored in an encrypted hard-drive by a single agent ([name]) who is the only researcher who has access to the randomization data.

5. Inclusion/Exclusion Criteria:

Please provide detailed description of inclusion and exclusion criteria. If a formal protocol for the study exists, page references to the protocol are acceptable.

Inclusion criteria:

1. Scheduled for pancreatic surgery requiring pancreatic resection at DHMC
2. Age greater than 18 years old
3. Ability to provide written informed consent

Exclusion criteria:

1. Inability to provide written informed consent
2. Current ongoing acute pancreatitis
3. Pregnant or nursing mothers
4. Any medical condition which in the judgment of the Investigator renders participation in this study medically inadvisable.
5. Participation in an investigational clinical study for a drug or medical device within 30 days prior to Visit 1.
6. [Any known allergy to methylene blue.](#)

6. Financial Considerations:

Disclosure of financial impact on the participant is critical to informed consent. Insurance cannot be billed for research-related services outside the standard of care or paid for by the funding agency for

the study. The department, the study or the participant may be responsible for payment for research-related services. Participants should know which tests, visits, or procedures will be billed to them or their insurance and which ones will be paid by the funding agency for the study or the department.

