CRF, and then building a multivariable logistic regression model using the categorical variable of drain amylase >3x the upper limit of normal. The data from the multivariate regression will be reported as Odds Ratios.

The secondary outcomes are both categorical and continuous variables and thus we will use the Fisher's Exact test as well as the two-tailed student's t-test. A multivariable analysis is not planned for evaluating the secondary variable.

Randomization will occur in a block format of 5 and will be generated by the primary investigators.

c) Justify the sample size, using the concepts of power, type I error, and effect size if applicable. If a formal protocol for the study exists, page references to the protocol are acceptable.

A clinically significant absolute decrease of 15% (20% to 5%) in the pancreatic duct leak rate. Based on these estimates and a two-tailed test comparing proportions using the statistical calculator (<http://homepage.stat.uiowa.edu/~rlenth/Power>), we project an estimated sample size of **176 participants (88 per arm)** to demonstrate an absolute 15% reduction in the leak rate with 80% power at a two-sided alpha level of 0.05.

8. Data and Safety Monitoring:

Describe plans for data and safety monitoring to ensure the safety of subjects and the quality of the data. As described in federal guidance "... a variety of types of monitoring may be anticipated depending on the nature, size, and complexity of the trial. In many cases, the principal investigator would be expected to perform the monitoring function." This plan should include monitoring to determine:

The progress of the trial, including periodic assessments of data quality and timeliness, participant recruitment, accrual and retention, participant risk versus benefit, and other factors that can affect study outcome. Monitoring should also consider factors external to the study when interpreting the data, such as scientific or therapeutic developments that may have an impact on the safety of the participants or the ethics of the study.

Note: This section does not request information related to sponsor study monitor visits. This section requires a description of an adequate data and safety monitoring plan.

Interim analysis will be performed once 50% (88) patients have been enrolled. If more than 66% of cases of duct leak are in a particular study group, a formal comparison between groups will be performed with the use of a two-sided stopping boundary of 0.005%.

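### Two operations are pooled without stratified randomisation or a stratified primary test; the plan is valid as it stands, but stratifying by operation type would cost almost nothing and protect balance

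*Combined protocol and SAP*

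**What the plan says.** Section 1 (Abstract) describes the population as "patients undergoing pancreatic resection (pancreaticoduodenectomy and distal pancreatectomy". The matching inclusion criterion in Section 5 is broader: "Scheduled for pancreatic surgery requiring pancreatic resection at DHMC". Section 4 recognises two kinds of leak site, because the surgeon is to "examine the anastomosis or repaired cut edge of the pancreas".

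Section 3C sets the allocation: "1/2 of the patients would receive intra-operative secretin, the other half would receive saline placebo". The only statement on method is at the end of Section 7b: "Randomization will occur in a block format of 5 and will be generated by the primary investigators". No stratification factor is named. Section 4 places randomisation during surgery, once the surgeon has accepted the reconstruction and before closure. It also lists operative technique among the items on the case report form (CRF).

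Section 7b makes a two-tailed Fisher's exact test the primary analysis, with no strata. It then plans a univariate screen of CRF variables and a multivariable logistic regression for drain amylase above three times the upper limit of normal. Section 7c sizes the trial on one pooled contrast: "A clinically significant absolute decrease of 15% (20% to 5%) in the pancreatic duct leak rate", giving "176 participants (88 per arm" "with 80% power at a two-sided alpha level of 0.05".

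**The concern.** The intervention works only if the surgeon sees a leak and closes it, and the site inspected is an anastomosis in one operation and a cut edge in the other. Operation type is therefore a plausible influence on leak risk and on the size of any effect. With one unstratified list the two arms can end up with different operation mixes by chance. If leak rates differ by operation, that difference moves the unadjusted comparison. The plan asks for no leak counts within operation, so a reader could not tell whether a result holds for both. All of this could be settled in advance, because the factor is known at the moment of randomisation.

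**Working it through.** **1. The plan's own sample size.** Inputs from Section 7c: 20% against 5%, two-sided alpha 0.05, power 80%. The mean proportion is 0.125.

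- Without correction: n0 = [1.96 × √(2 × 0.125 × 0.875) + 0.842 × √(0.20 × 0.80 + 0.05 × 0.95)]² / 0.15² = 75.12 per arm.
- With continuity correction: n = (n0/4) × [1 + √(1 + 4/(n0 × 0.15))]² = 87.95, so 88 per arm.

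The stated 88 per arm is reproduced.

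**2. The planned test at that size.** Exact enumeration of Fisher's test at 88 per arm gives 83.8% power for 20% against 5%. Its type I error at a common 20% leak rate is about 3.2%.

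**3. Chance imbalance in operation mix.** The documents give no case mix, so assume one third distal.

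- SD of the between-arm difference = √(2 × (1/3) × (2/3) / 88) = 7.1 points.
- The normal approximation puts the chance of a difference of 10 points or more at 16%. Exact counting with 88 per arm gives about 17%.
- If one operation makes up 50%, 60% or 70% of cases, the exact figures are 17.5%, 16.6% and 18.8%. A difference of 15 points or more has a chance of about 2-5%.

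**4. What an imbalance does to the estimate.** The documents give no leak rates by operation, so assume control rates of 15% and 30% (gap 15) or 12% and 36% (gap 24). Both average 20% at a 2:1 mix. The shift is imbalance × gap:

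- 0.10 × 15 = 1.5 points
- 0.10 × 24 = 2.4 points

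These figures take the same gap in both arms. If secretin cut leaks by 75% in both operations, the average gap would be smaller: 0.10 × (15 + 3.75)/2 = 0.9 points and 0.10 × (24 + 6)/2 = 1.5 points. The target effect is 15 points.

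**5. Power, with the two changes separated.** Simulated trials (100,000 per row), 176 patients, one third distal, 75% relative reduction. CMH is run with stratified randomisation, the other two tests without.

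| Control leak rates | Fisher (as planned) | Pooled chi-square | CMH, uncorrected | CMH, continuity-corrected |
|---|---|---|---|---|
| 20% / 20% | 83.7% | 88.2% | 88.3% | 82.1% |
| 15% / 30% | 83.6% | 88.2% | 88.8% | 82.9% |
| 12% / 36% | 83.8% | 88.3% | 89.6% | 84.1% |

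- Dropping Fisher's test (column 2 to column 3): 4.5, 4.6 and 4.5 points.
- Stratifying (column 3 to column 4): 0.1, 0.6 and 1.3 points.
- In a separate run with a common odds ratio and a 30-point gap, stratifying took power from about 88.3% to 90.7%, a gain of 2.4 points.
- Simulated type I error of the uncorrected CMH test is 4.9-5.0%.

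**6. The two halves belong together.** If randomisation is stratified but the unadjusted Fisher test is kept, its type I error falls to about 2.1% at a 30-point gap. Stratified lists therefore need a stratified test.

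**The case against.** The strongest reply is that nothing here is broken. An unstratified Fisher test in a single-centre randomised trial of 176 patients is a defensible choice, chance imbalance does not inflate its type I error, and power exceeds the stated 80%. That stands.

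A reader might infer that lack of stratification costs about 5 or 6 points of power. The working does not support this. Most of that gap appears even when both operations have a 20% leak rate, where operation type carries no information, so it comes from Fisher's conservatism. A continuity-corrected CMH test would give no material gain and in two of the three rows would lose power.

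A reader might also take operation type to be an established risk factor. The documents do not say so. They give one leak rate, about 20%, for all resections, and a different leak site does not by itself mean a different risk. With no difference in risk, an imbalance does no harm to the estimate.

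The planned logistic regression could adjust for operation type, since operative technique is on the CRF. It is only a partial answer. It is not the primary test, its covariates follow a univariate screen, and nothing requires operation type to enter. Its outcome is also the amylase threshold alone, whereas the leak definition in Section 4 adds a clinically relevant condition.

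**Conclusion.** The point holds as a cheap improvement to a valid plan. The firm part is structural: operation type is known at randomisation, yet neither the allocation nor the primary test uses it. The balance argument rests on an assumed mix of one third distal (about a 17% chance of a 10-point difference) and on assumed leak-rate gaps of 15 to 24 points (a shift of about 1.5 to 2.4 points, less if secretin narrows the gap). The full change takes power from about 84% to about 88-90%. Roughly 4.5 points belong to the change of test and about 0 to 1 to stratification, or about 2.4 at an extreme 30-point gap. The case for stratifying is therefore balance and interpretability, with power a secondary benefit that depends on the form of test chosen.

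**What to change.** In Section 7b:

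- Use one permuted-block list per operation type, with a block size that can be split 1:1. A block of 5 cannot, so the scheme needs rewriting in any case. Section 5 admits any pancreatic resection, so state which list takes an operation that is neither of the two named.
- Make the primary test a CMH test by operation type, stated to be without continuity correction.
- Report a stratified risk difference with its 95% confidence interval, and leak counts by arm within each operation.

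The cost is one extra list and a few lines of text, with no additional patients. There are two downsides: one incomplete block per stratum at the end, and an asymptotic test in place of an exact one (simulated type I error about 5%).
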